1.9 Petabytes of NAS centralized disk storage

1.2 Petabytes of off-site storage for disaster recovery

400 Terabytes of encrypted storage for scientific workloads

Nightly backups, snapshots, and off-site data retention

2.4Ghz / 5Ghz secure wireless network

1 Gbit/s commodity Ethernet network

Data Analysis Tools: MATLAB, SPM, AFNI, FSL, MRIcro, xjView, R, SAS, Graphpad Prism, SPSS

Productivity Tools: Adobe Suite, Microsoft Office Suite, vi, vim, emacs, etc.

MRI Scanning Resources (FBRI):

Virginia Tech has three research-dedicated Siemens 3T MR scanners (2 Siemens Magnetom TIM Trios, and 1 PRISMA-FIT) available. Each scanner bay is equipped with the following stimulation and response interfaces:

behavioral response: two-hand, eight-button optical response pads with USB, serial, and TTL output (Current Designs, Inc.) video stimulation: rear-projection video display (Hitachi CP-SX635) corrective lenses for use with video stimulation: MR-compatible frames with insertable polycarbonate lenses (prescriptions range from -8.00 to +8.00)

(Solo Bambini) stimulus delivery: dedicated computers for experiment presentation (Dell Optiplex 980) audio delivery: MRI compatible headphones.

CT Scanning Resources (FBRI):

Virginia Tech has a Siemens Somatom Confidence RT Pro CT Scanner available.

Mental Health Resources: In the unlikely and unexpected event that a participant requires or requests mental health resources, the research staff will offer a national mental health hotline number (National Alliance on Mental Illness helpline: [name]). Those staff and volunteers are trained to transfer calls to crisis management, if needed or work to answer questions about education programs, treatment options, symptoms of mental health conditions and more (additional information may be found here: <https://www.nami.org/find-support/nami-helpline>). In the event of a mental health or other emergency, the local hospital system, Carilion Clinic is located approximately 1 mile from the FBRI and is accessible by the public.

Training: Study staff are trained in Human Research Protections through approved programs, such as CITI. Additionally, study procedures, such as participant task instructions, staff instructions to introduce and/or present and start computer tasks, and visit checklists are developed for each study in order to maintain consistency across participants and ensure all procedures are completed and documented. All staff consenting and administering research tasks review both the approved protocol and consent form prior to study startup and participant recruitment. If there are amendments or changes, staff review the new documents. Study coordinators review the consent process and procedures on an ongoing basis.

27.0 Multi-Site Research

Contact the HRPP for multi-site research (involving multiple institutions) and the details required for this section will be provided. Otherwise, indicate N/A.

N/A

Investigation of Low-intensity Focused Ultrasound Parameters

NCT: NCT05134233

09/12/2024

Statistical Analysis Plan (SAP) for ClinicalTrials.gov Submission

Study Title: Investigating Neuromodulatory Effects of Low-Intensity Focused Ultrasound (LIFU) in Humans

1. Objective:

This study aims to assess the effects of varying parameters of low-intensity focused ultrasound (LIFU)—such as intensity, duration, duty cycle, and pulsing—on neuromodulation in the human brain. The primary focus is on evaluating changes in motor-evoked potential (MEP) amplitude when LIFU is applied concurrently with transcranial magnetic stimulation (TMS).

2. Study Design:

2.1 Interventions:

The study involves the application of LIFU using the following 20 parameter combinations:

- **Intensity levels:** 6 W/cm² and 24 W/cm²
- **Duty cycles:** 1%, 10%, 30%, 50%, and 70%
- **Durations:** 100 ms and 500 ms
- **Pulsing conditions:** Pulsed versus continuous delivery evaluated in 4 combinations

2.2 Study Type:

This is a fully parameterized, repeated measures design in which LIFU is delivered concurrently with TMS. Each subject experiences all combinations of LIFU parameters.

2.3 Data Collection:

- **MEP amplitude:** Measured as the peak-to-peak response for each LIFU parameter combination, with 20 stimulations per trial per subject.
- **Normalized MEP values:** Calculated by normalizing MEP amplitudes for each parameter combination to baseline (pre-LIFU) values.

3. Outcome Measures:

3.1 Primary Outcome Measure:

- **MEP Amplitude:** Normalized MEP amplitude, analyzed across the 20 parameter combinations of LIFU.

3.2 Secondary Outcome Measure:

- **Pulsed vs. Continuous Ultrasound:** Effects of pulsing on MEP amplitude will be evaluated.

4. Statistical Analysis Plan:

4.1 Power Analysis:

Based on preliminary data from a pilot study (N=5), we observed maximal changes in MEP amplitude of:

- **Excitatory effects:** 46.35% \pm 12.33%
- **Inhibitory effects:** -25.54% \pm 15.56%

- **Minimal effects:** $5.99\% \pm 7.87\%$ with less optimal parameter combinations.

To detect a meaningful change in MEP amplitude, we calculated a required sample size of **N=56 participants**. This is sufficient to detect a **15% change** in MEP amplitude (minimum clinically significant change) with a power of **0.8** and a significance level of **p = 0.05**. This sample size may not detect minimal changes (~6%), but is adequate to capture meaningful excitatory and inhibitory effects across parameter combinations.

4.2 Assumptions Testing:

- **Normality of MEP Amplitudes:** Tested using **Bartlett's test for sphericity** ($p < 0.05$). If assumptions of normality or homogeneity of variances are violated, non-parametric tests will be used.

4.3 Primary Analysis:

- **Paired t-tests:** We will compare baseline normalized MEP values with post-intervention MEP values for each LIFU parameter combination. To control for multiple comparisons, a **Bonferroni correction** will be applied, adjusting the significance level to **p < 0.0025** ($0.05/20$).
- **Three-Way Repeated Measures ANOVA:** A 3-way repeated measures ANOVA will be performed to assess the main effects and interactions between the following factors:
 - **Intensity:** 6 W/cm² vs. 24 W/cm²
 - **Duty Cycle:** 1%, 10%, 30%, 50%, 70%
 - **Duration:** 100 ms vs. 500 ms
- **Post-hoc testing:** If significant main effects or interactions are observed, **Tukey's Honest Significant Difference (HSD) test** will be applied for pairwise comparisons. Tukey's HSD will control the family-wise error rate, ensuring reliable comparisons between parameter combinations.

4.4 Pulsed vs. Continuous Analysis:

A separate **three-way repeated measures ANOVA** will be conducted to evaluate differences between pulsed and continuous LIFU delivery. The main factors assessed will be:

- **Intensity:** 6 W/cm² vs. 24 W/cm²
- **Number of Cycles:** 35,000 vs. 75,000
- **Pulsing Condition:** Pulsed vs. Continuous

Post-hoc analyses using **Tukey's HSD** will follow if significant results are observed.

5. Handling Missing Data:

If missing data arises, participants with missing measurements for key outcomes will be excluded from specific analyses. However, where possible, **multiple imputation** methods will be used to handle missing data. Sensitivity analyses will be conducted to assess the robustness of the results in the presence of missing data.

6. Assumptions and Corrections:

6.1 Assumptions for Parametric Testing:

- **Normality and sphericity:** The normality of MEP data will be confirmed via **Bartlett's test** ($p < 0.05$). If normality or homogeneity of variances is not met, non-parametric alternatives will be used, such as the **Wilcoxon signed-rank test**.

6.2 Correction for Multiple Comparisons:

- **Bonferroni correction** will be applied to paired t-tests, adjusting the significance level to $p < 0.0025$ for each comparison (0.05/20 combinations).

7. Data Presentation and Reporting:

Results will be presented as **mean \pm standard deviation (SD)** for each LIFU parameter combination. Data will be visually represented using bar charts and line graphs for MEP amplitudes, with appropriate error bars. The statistical significance of comparisons will be indicated with asterisks (* $p < 0.05$, ** $p < 0.0025$, etc.).

Results from the ANOVAs, including F-values, degrees of freedom, and p-values, will be reported in tables. Post-hoc comparisons using Tukey's HSD will be detailed with adjusted p-values.

8. Conclusion:

The analysis plan outlined above ensures a robust statistical approach to evaluating the effects of various LIFU parameters on MEP amplitude, providing insights into how different ultrasound intensities, duty cycles, durations, and pulsing patterns influence neuromodulatory outcomes. These findings will contribute to optimizing LIFU for potential therapeutic applications in neuromodulation.

This SAP has been designed to ensure comprehensive evaluation of the hypotheses, with appropriate statistical rigor to control for errors and variability across conditions.

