2.0 Objectives

2.1 *Describe the purpose, specific aims, or objectives of this study:*

An understanding of the interaction of ultrasound parameters on human brain function is critical to rationally design clinically useful therapeutic methods that result in predictable outcomes. Experiments in small and large animal are confounded by small cranial vault size, anesthesia and thinner and differently shaped skulls making translation to human uncertain. Human studies remove translation and scaling issues and can be directly related for clinical use. Here, we will systematically test ranges of ultrasound parameters (intensity, duration, duty cycle, pulse repetition frequency) in a fully parametric design delivered to the primary motor cortex (M1) in healthy human volunteers. This will allow for an evaluation of what parameters change effect (and by how much), and determine how they interact with other parameters. Studies will be conducted in a cortical brain area using different outcome measures to test robustness and reproducibility.

2.2 *State the hypotheses to be tested:*

We hypothesize that duty cycles between 10 and 30% will result in inhibition and duty cycles > 50% will result in excitation independent of intensity and duration. We further hypothesize that longer durations will result in inhibition whereas shorter duration will

results in excitation. Finally, we hypothesize that 1000 Hz is the optimal PRF for these effects.

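### SAP 4.2 and 6.1 make Bartlett's test the normality check that switches the primary analyses; it does not test normality, and the plan is inconsistent on whether the factorial ANOVA survives a failed check

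*SAP*

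**What the plan says.** SAP 4.2, under a label naming normality of MEP amplitudes, says "Tested using Bartlett's test for sphericity ($p < 0.05", and then: "If assumptions of normality or homogeneity of variances are violated, non-parametric tests will be used". SAP 6.1, under a label naming both normality and sphericity, says "The normality of MEP data will be confirmed via Bartlett's test ($p < 0.05" without stating which of Bartlett's tests is meant. It continues "If normality or homogeneity of variances is not met, non-parametric alternatives will be used, such as the" and gives the Wilcoxon signed-rank test as its example.

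The design is within-subject (SAP 2.2): "Each subject experiences all combinations of LIFU parameters". The primary analyses in SAP 4.3 are 20 paired t-tests at 0.0025 and a 2×5×2 repeated-measures ANOVA (intensity, duty cycle, duration). SAP 4.3 states "A 3-way repeated measures ANOVA will be performed to assess the main effects and interactions", and SAP section 7 states "Results from the ANOVAs, including F-values, degrees of freedom, and p-values, will be reported in tables". Neither statement depends on the assumption check. Tukey's HSD follows significant terms. The documents contain no check of normality on paired differences or residuals, no repeated-measures sphericity correction, and no factorial non-parametric method.

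**The concern.** An assumption check that decides how the primary outcome is analysed should respond to the assumption in question. Bartlett's test for sphericity has as its null hypothesis that the correlation matrix is the identity. Repeated-measures sphericity is a different condition: equal variances of the differences between levels. Equally correlated, equal-variance normal data satisfy every assumption of the planned ANOVA, yet they violate the null hypothesis of this test.

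Two things are at stake. First, valid t-tests could be replaced by rank tests for a reason unrelated to normality, and with skewed data that changes what is tested from a mean to something else. Second, after a failed check the SAP can be read in two ways for duty cycle and its three interactions. Either the ANOVA goes ahead, as 4.3 and section 7 say, or it is replaced by a method that is not named. That choice would then be made with the data in hand.

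These four terms show whether the effect differs between duty-cycle levels and whether it depends on intensity and duration. Protocol 2.2 hypothesises that "duty cycles between 10 and 30% will result in inhibition and duty cycles > 50% will result in excitation", and that this does not depend on intensity or duration. The directions of change from baseline are tested by the paired comparisons. The claim of independence rests on the interactions.

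**Working it through.** **Inputs from the documents.** 20 conditions (2×5×2) and 56 analysed subjects. The plan's own figures agree here: 0.05/20 = 0.0025, and 80 enrolled × 0.70 completing = 56 (Protocol 14.1). The documents give no between-condition correlation and no distribution shape, so both are varied as assumptions.

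**1. What the named test responds to.** The statistic is −(n − 1 − (2p + 5)/6) × ln|R| on p(p − 1)/2 df. With n = 56 and p = 20 the multiplier is 55 − 45/6 = 47.5 and the df are 20 × 19/2 = 190. The 5% critical value is 223.2.

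Under a common correlation r, ln|R| = 19 ln(1 − r) + ln(1 + 19r). The amount by which correlation alone raises the statistic above its null mean of about 190 is therefore roughly:

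- r = 0.1: 47.5 × 0.937 = 44.5, giving about 235
- r = 0.2: 47.5 × 2.671 = 126.9, giving about 317
- r = 0.3: 47.5 × 4.875 = 231.5, giving about 422

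All three exceed 223.2, although the data are exactly normal.

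**2. Simulated rejection** (n = 56, 20 conditions; ranges are across repeated simulations).

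| Data | Rejected |
|---|---|
| Normal, r = 0 | 5–6% |
| Normal, r = 0.05 | 21–22% |
| Normal, r = 0.1 | 66–70% |
| Normal, r = 0.15 | 95% |
| Normal, r = 0.2 | 99.5% or more |
| Normal, r = 0.3 | 100% |
| Lognormal, uncorrelated, log-SD 0.25 | 6–7% |
| Lognormal, uncorrelated, log-SD 0.5 | 7% |
| Lognormal, uncorrelated, log-SD 1.0 | 16–18% |

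On normal data with r = 0.3, where the check always fails, the duty-cycle F-test on 4 and 220 df has a simulated type I error of 4.9%. The check would discard a valid analysis.

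**3. Is a correlation of 0.2 plausible?** SAP 2.3 divides each condition by baseline. If one baseline mean of 20 pulses is shared by all of a subject's conditions (an assumption), numerator and denominator carry about equal error variance. The induced correlation is then about 1/(1 + 1) = 0.5; simulation gives 0.51–0.53 for pulse CVs of 0.3–0.7. A separate baseline for each condition would not induce this. The SAP does not say which applies.

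**4. If 6.1 means Bartlett's variance test.** That test assumes independent groups. On normal, equal-variance data it rejects about 4–5% at r = 0–0.1 but only 0.3–0.7% at r = 0.5. On lognormal data (r = 0 or 0.3) it rejects about 25–38% at log-SD 0.25, 92–96% at 0.5 and 100% at 1.0. It also rejects 100% of the time when SDs run from 7.87 to 15.56. It therefore mixes skew with unequal variances.

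**5. What the switch costs in the paired tests** (level 0.0025, t versus Wilcoxon).

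- Normal differences: power 44% vs 40% at 0.4 SD, and 82% vs 78% at 0.55 SD.
- Lognormal, log-SD 0.25, at the SAP's 15% target: 77% vs 65% for +15%, and 95% vs 97% for −15%.
- Lognormal with no change in the mean (nominal 0.25%): about 0.4% vs 0.6% at log-SD 0.25, 0.6% vs 2.0% at 0.5, and 2.7% vs 16.7% at 1.0.
- Lognormal with the median unchanged, log-SD 0.25: the order reverses, 0.8% vs 0.35%.

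**6. What the fallback can reach.** Duty cycle has 5 − 1 = 4 df, and so does each of its three interactions, because the other factors have two levels (4 × 1 = 4; 4 × 1 × 1 = 4). A signed-rank test addresses one paired contrast, so it gives no joint test of these four terms.

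**7. Secondary point: no sphericity correction.** Type I error of the duty-cycle terms at nominal 5%, uncorrected versus Greenhouse-Geisser:

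- 5.2–6.3% vs 4.1–4.9% if the pilot ± values are SDs spread over the five duty-cycle levels
- 4.8–5.5% vs 4.2–4.8% if they are spread over all 20 conditions
- 7.0–7.9% vs 4.5–5.1% under an assumed autoregressive correlation of 0.8 along duty cycle

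One-df terms are unaffected.

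**The case against.** Both switch sentences speak of normality or homogeneity of variances, not correlation, and 6.1 says only Bartlett's test. A misnamed variance test is therefore a fair reading, and on that reading the check responds to skew and seldom fires on normal, equal-variance data. This stands as a limit on the size of the problem. It does not rescue the rule: 4.2 names the sphericity version, and the variance test presumes independent groups and is not a normality test either.

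A reader might infer that this design would nearly always fail the check. The documents do not support that without qualification. They give no correlation, they do not say that the test is applied jointly to all 20 conditions, and they leave unclear which side of 0.05 counts as a pass. If a small p counted as a pass, correlated data would nearly always pass, which is no more informative.

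A reader might also infer that the duty-cycle terms are left without any test. That goes too far. SAP 4.3 and section 7 present the ANOVA as unconditional, and Wilcoxon is offered only as an example. What stands is that the sections conflict and that no factorial alternative is named.

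Finally, a pre-specified valid check on the paired differences, with a named factorial fallback, would also cure the defect. Removing the switch is the simpler remedy but not the only one.

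**Conclusion.** The point holds as a mis-specified assumption check with an incomplete and inconsistent fallback. On the wording of 4.2, the check rejects perfectly normal data about 70% of the time at correlation 0.1 and at least 99% at 0.2 or more. This assumes 56 subjects, 20 conditions tested jointly and a common correlation. It barely detects non-normality in uncorrelated data. Neither version of Bartlett's test is a valid normality check here.

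Severity is moderate: it should be fixed. It might be read as undermining the whole primary analysis or the first hypothesis, but the figures do not bear that out. For normal differences the switch costs about 4 points of power. The predicted directions of change are tested by the paired comparisons, for which Wilcoxon is a usable substitute. The larger error rates need a log-SD of 1.0, which nothing in the documents establishes. The missing sphericity correction is secondary and modest: about 5–6% on the pilot spreads, and 7–8% only under the assumed strong serial correlation.

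**What to change.** - Delete the Bartlett check and the switch sentence from SAP 4.2 and 6.1.
- State in 4.3 that the 20 paired t-tests and the 2×5×2 repeated-measures ANOVA are run regardless, with Greenhouse-Geisser-corrected F-tests for duty cycle and its three interactions.
- Replace pooled-error Tukey HSD for duty-cycle comparisons with paired differences and a multiplicity adjustment such as Holm, because the pooled error relies on the same sphericity condition as the uncorrected F-tests.
- Examine the paired differences and ANOVA residuals descriptively, for example with Q-Q plots, without switching the test.
- Report Wilcoxon signed-rank beside the paired t-tests as a sensitivity analysis.

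The cost is SAP wording and a software option; data collection, sample size and outcome do not change. Duty-cycle p-values become slightly larger. If normalised MEPs are strongly skewed, the retained t-tests exceed their nominal 0.25% for a mean null: about 0.6% at log-SD 0.5, against about 2% for Wilcoxon, and 2.7% against 16.7% at log-SD 1.0. Under the same skew the corrected duty-cycle F-tests stay below 5%: 4.2–4.8% at log-SD 0.25–0.5 and 2.9–3.8% at 1.0.

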4.0 Study Endpoints

- 4.1 *Describe the primary and secondary **study** endpoints. See links below for discussion of study endpoints and how they may differ from study objectives. These are most common in clinical trials but are sometimes applicable to other types of biomedical research, as well as social, behavioral, or educational research. See link below for a discussion.*

https://docs.google.com/document/d/1Wocz7K7a0hCQJPPO_khh511SQQjhGDDGHzcOPRHR5Tw/edit?usp=sharing

Primary endpoint: Waveform combinations that induce reliable excitation and inhibition

Secondary endpoint: Documentation of tolerability of waveforms

- 4.2 *Describe any primary or secondary **safety** endpoints. These should be included for all studies that are greater than minimal risk. (Minimal risk: The probability and magnitude of harm or discomfort anticipated in the research that are not greater in and of themselves than those ordinarily encountered in daily life or during the performance of routine physical or psychological examinations or tests.):*

Primary safety endpoint: Subjective report questionnaire on neurological/physiological feelings.

Participants can request study procedures be stopped at any point throughout the experiment.

Based upon previous literature from our lab in humans we expect the LIFU effect to last up to 30 minutes. There is no evidence as yet that the proposed administration lasts longer than 30 minutes. All participants will be involved in laboratory procedures during this interval and be queried via the attached Report of Symptoms Questionnaire for any signs or symptoms from the LIFU intervention pre and post intervention.

Post-stimulation Monitoring:

Participants will be monitored for at least 30 minutes after stimulation has ended.

Participants will complete a Report of Symptoms questionnaire prior to leaving the facility. Responses will be monitored with each given session and the change of any symptom to 'severe' on the post-stimulation questionnaire compared to the pre-stimulation questionnaire will require PI evaluation.

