14.0 Number of Subjects

- 14.1 Indicate the total number of subjects to be enrolled and how this number was determined (e.g., sample size calculation [show], number of available subjects in a finite pool, number of tests funding award would allow):*

We anticipate enrolling 80 subjects in this study. This population size should allow for adequate statistical significance and analysis.

It is anticipated that 70 percent of participants will complete the study sessions. To account for this we anticipate enrolling 80 participants to yield approximately 56 participants.

Based upon preliminary data ($N = 5$) and only two variables (duty cycle and duration) we found maximal changes of motor evoked potential amplitudes of $46.35\% \pm 12.33$ and $-25.54\% \pm 15.56$ depending upon variable selection. Minimal changes with change of variables was 5.99 ± 7.87 . We propose an $N = 56$ and while N is not sufficient to detect a statistically significantly difference of $\sim 6\%$ an $N = 56$ is sufficient with a power of 0.8 and a $p = 0.05$ to detect a $\sim 15\%$ that we suggest is the minimal significant change that is required for potentially clinically significant change.

- 14.2 If this is a multi-site study, indicate the number of subjects to be enrolled at this site and the total to be enrolled from all sites:*

N/A

- 14.3 If applicable, indicate the number of potential subjects you expect to screen for enrollment, and the number of subjects you will need to complete the research procedures:*

It is anticipated that 70 percent of participants will complete the study sessions. To account for this we anticipate enrolling 80 participants to yield approximately 56 participants.

14.4 If the study has more than one procedure, indicate the total number of subjects to undergo each procedure separately:

It is anticipated that all participants will complete all study procedures, given subject interest.

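### Single-step Bonferroni on the 20 primary cell tests is valid, but Holm gives the same family-wise guarantee and rejects at least as many hypotheses

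*SAP*

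**What the plan says.** SAP 2.1 defines the test conditions: "The study involves the application of LIFU using the following 20 parameter combinations", a grid of 2 intensities, 5 duty cycles and 2 durations. SAP 3.1 gives the primary outcome as "Normalized MEP amplitude, analyzed across the 20 parameter combinations of LIFU".

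The first primary analysis in SAP 4.3 is a set of paired t-tests: "We will compare baseline normalized MEP values with post-intervention MEP values for each LIFU parameter combination". The same item continues "To control for multiple comparisons, a" Bonferroni correction is used at p < 0.0025. SAP 6.2 repeats that the correction "will be applied to paired t-tests, adjusting the significance level to" p < 0.0025, obtained as 0.05/20.

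SAP 7 reports cell means with SDs and marks significance with asterisks, the double asterisk standing for p < 0.0025. It plans no confidence intervals for the cells.

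Protocol 4.1 names the primary endpoint as "Waveform combinations that induce reliable excitation and inhibition".

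**The concern.** The result of the primary analysis is a list of waveforms, and the rejection rule decides which cells go on it. Single-step Bonferroni holds every cell at 0.0025 whatever the other 19 show. That is most conservative when many cells have a true effect, and the sponsor expects many.

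- **Hypothesis (Protocol 2.2).** Inhibition is expected at duty cycles of 10 to 30% and excitation above 50%, whatever the intensity or duration.
- **Pilot (Protocol 3.2).** Inhibition of about 10-15% is reported at a 30% duty cycle, and facilitation of about 15-25% at 50 to 70%.

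Holm needs no added assumption about how the cells are correlated. This matters because each subject receives every combination. At stake are true waveforms left off the list although the 0.05 family-wise guarantee would have allowed them on.

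**Working it through.** **1. The plan's own figure.** 0.05/20 = 0.0025, as stated. With 20 independent true nulls, the family-wise error is 1 - (1 - 0.0025)^20 = 0.0488, within 0.05.

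**2. Holm.** Order the 20 p-values and compare the k-th smallest with 0.05/(20 - k + 1). Stop at the first failure. The thresholds run 0.0025, 0.00263, 0.00278, ..., 0.005 (11th), ..., 0.025, 0.05. No threshold is below 0.0025, so Holm rejects every cell that Bonferroni rejects. After 12 rejections the next threshold is 0.05/8 = 0.00625; after 16 it is 0.05/4 = 0.0125.

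**3. Number of active cells (assumption).** The pilot supports inhibition at 30% and facilitation at 50 and 70%. That is 3 duty cycles x 2 intensities x 2 durations = 12 cells. Adding 10%, which is hypothesised but not reported from the pilot, gives 4 x 2 x 2 = 16.

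**4. SD (assumption).** SAP 4.1 gives pilot values (N = 5) with ± 12.33 and ± 15.56, without saying whether these are SDs or standard errors.
- 15.56 read as an SD: 15.56.
- Read as standard errors: 12.33 x √5 = 27.57 and 15.56 x √5 = 34.79.
- SD implied by N = 56, a 15% change, power 0.8 and two-sided p = 0.05 in a paired t-test: 39.36.

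**5. Simulation.** The settings were 10,000 trials per row, N = 56, two-sided paired t-tests on percentage change (55 df) and equal between-cell correlation of 0.4. Effects were -12.5% at 30% duty cycle (and at 10% where active), +20% at 50 and 70%, and none elsewhere. Sidedness is not stated in the SAP; two-sided is assumed.

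| Active cells | SD (%) | Power per active cell, Bonferroni to Holm | Extra true cells | Family-wise error, Bonferroni to Holm |
|---|---|---|---|---|
| 12 | 15.56 | 0.999 to 1.000 | 0.01 | 0.018 to 0.040 |
| 12 | 27.57 | 0.85 to 0.89 | 0.40 | 0.017 to 0.032 |
| 12 | 34.79 | 0.69 to 0.73 | 0.55 | 0.018 to 0.031 |
| 12 | 39.36 | 0.57 to 0.61 | 0.51 | 0.018 to 0.028 |
| 16 | 15.56 | 0.998 to 1.000 | 0.02 | 0.010 to 0.044 |
| 16 | 27.57 | 0.79 to 0.86 | 1.1 | 0.009 to 0.028 |
| 16 | 34.79 | 0.60 to 0.67 | 1.2 | 0.010 to 0.022 |
| 16 | 39.36 | 0.48 to 0.54 | 0.9 | 0.010 to 0.017 |

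In every simulated trial Holm's rejections contained Bonferroni's.

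**6. Sensitivity.** With 16 active cells and weaker effects (-10% and +15%), power per active cell goes from 0.97 to 0.99 at SD 15.56, from 0.58 to 0.65 at 27.57, and from 0.25 to 0.27 at 39.36. With a 15% effect in each active cell (correlation 0 or 0.5) and SDs of 27.57 to 39.36, the gain is 0.00 cells with 1 active, 0.05-0.08 with 5, and 1.6-3.0 with all 20.

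**The case against.** The strongest reply is that nothing in the SAP is wrong. The arithmetic is right, the correction controls family-wise error, and choosing Holm is a preference for efficiency. That stands: a reader might infer that Bonferroni is a mistake here, and the documents do not support that.

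Three further points limit the claim.

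- **Size of the gain.** A reader might take the pilot to show inhibition across 10 to 30%, which would make 16 cells active. Protocol 3.2 reports inhibition only at 30% and adds that duty cycle interacts with duration, so even 12 is not assured. With 12 cells the gain is roughly half that with 16. The larger SDs are readings of the pilot values or solved back from N = 56; none is stated.
- **Not free in realised error.** It is tempting to say that Holm identifies more true waveforms at no cost. It identifies at least as many, and the nominal bound is unchanged, but the actual chance of a false entry moves closer to 0.05. At SD 15.56 with 16 active cells it rises from 0.010 to 0.044 for 0.02 extra true cells. Since the endpoint asks for reliable effects, a sponsor could reasonably prefer the stricter rule.
- **Power.** Protocol 14.1 says that N = 56 "is sufficient with a power of 0.8 and a $p = 0.05$ to detect a" change of about 15%, but the tests run at 0.0025. At the implied SD of 39.36, power for a 15% effect in one cell falls from 0.80 to 0.39. A reader might think that Holm repairs this. It does not, because its first step is still 0.0025.

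The usual reason for keeping single-step Bonferroni is to have matching simultaneous intervals. The SAP plans none, so that defence is not available here.

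**Conclusion.** The point holds as an optional efficiency gain of low priority. What is certain is mathematical: Holm has the same 0.05 family-wise bound under any dependence, never rejects less, and needs no more participants.

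The size is conditional on the assumptions above. At SDs of 27.6 to 39.4%, expect about 0.4 to 0.55 extra true waveforms with the 12 pilot-supported cells active, and about 0.9 to 1.2 with 16. At SD 15.6% under the same effects, or with few active cells, expect almost none. The price is a higher realised family-wise error that remains within the bound.

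**What to change.** Before results are seen:

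- **SAP 4.3 and 6.2.** Replace the fixed level of 0.0025 with the Holm step-down procedure at family-wise 0.05 over the 20 tests, and report Holm-adjusted p-values. The procedure works on p-values, so it also applies if the Wilcoxon alternative in SAP 6.1 is used.
- **SAP 7.** Redefine the double asterisk as Holm-adjusted p < 0.05, and say that the single asterisk is unadjusted.
- **Intervals.** If Bonferroni intervals (99.75% per cell) are also shown, state that one may include no change for a cell that Holm rejects.

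The cost is a sentence in each of two sections and one symbol definition, with no new data or participants. The sponsor should accept knowingly the rise in realised error within the bound. The power statement needs its own correction.
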